## ***Template Instructions***

### ***Sections that do not apply:***

- *In several sections, the addition of checkboxes for **Not Applicable** have been added to the template as responses.*
  - *If an N/A checkbox is present, select the appropriate justification from the list.*
  - *If an N/A checkbox is not present, or if none of the existing checkboxes apply to your study, you must write in your own justification.*
- *In addition:*
  - *For research where the only study procedures are records/chart review: Sections 6, 21, 22, 24, 25, 26 and 27 do not apply.*
  - *For exempt research: Section 6 may not apply. Section 6.1 will still apply if there is a study intervention.*

### ***Studies with multiple participant groups:***

- *If this study involves multiple participant groups (e.g. parents and children), provide information in applicable sections for each participant group. Clearly label responses when they differ. For example:*

#### **Response Example**

Intervention Group:

Control Group:

### ***Formatting:***

- *Do not remove template instructions or section headings when they do not apply to your study.*

*If you are pasting information from other documents using the “Merge Formatting” Paste option will maintain the formatting of the response boxes.*

### ***Amendments:***

- *When making modifications or revisions to this and other documents, use the **Track Changes** function in Microsoft Word.*
- *Update the version date or number **on Page 3**.*

## VERSION NUMBER/DATE:

*Include the version number and date of this protocol.*

Response:

Version 1 - January 5, 2023

Version 2 – January 6, 2023

Version 3 – January 11, 2023

Version 4 – January 31, 2023

## REVISION HISTORY

Revision #	Version Date	Summary of Changes	Consent Change?
1	1/6/23	Changed sections related to waiver of consent to reflect our actual consent processes.	Yes
2	1/11/23	Added our research assistant, [name], to the template.	No
3	1/31/23	Added [name] to section 16.2.	Yes

		
Clarified language about the US Bank cash gift cards in sections 12.1 and 27.1
 
Small clarification regarding the two samples in 12.1.
 
Clarified mechanism for participants to receive continuing education credit in section 24.1
	

## FUNDING:

*Indicate any funding for this proposal. This should match the Funding Sources page in Click IRB.*

Response:

We have been awarded funding for this project through the UB Clinical and Translational Science Institute (CTSI).

## GRANT APPLICABILITY:

*Indicate whether this protocol is funded by a grant (e.g. NIH, foundation grant). For a grant with multiple aims, indicate which aims are covered by this research proposal.*

*NOTE: This question does not apply to studies funded by a sponsor contract.*

*Include a copy of the grant proposal with your submission.*

Response:

All aims in this study will be funded by the CTSI grant.

## RESEARCH REPOSITORY:

*Indicate where the research files will be kept, including when the study has been closed. The repository should include, at minimum, copies of IRB correspondence (approval, determination letters) as well as signed consent documents. This documentation should be maintained for 3 years after the study has been closed.*

Response:

All files, IRB documentation, digital evidence of informed consent, and downloaded survey responses will be stored electronically on the secured UB Box server. Files will be accessed on the password-protected computer drive of the principal investigator.

*Location: [name] office. Baldy Hall*

*Address: [name]*

## Study Summary

Study Title	Evaluating the Social Workers Addressing Firearm Risk (SAFR) Intervention: A Pilot Study
Study Design	Aim 1: Repeated surveys (two time points)  Aim 2: Randomized controlled trial with pre-, post-, and follow-up tests.
Primary Objective	To evaluate the feasibility, acceptability, and preliminary effectiveness of the Social Workers Addressing Firearm Risk (SAFR) Intervention.
Secondary Objective(s)	Develop measurement tools to be used in the evaluation of the SAFR intervention.
Research Intervention(s)/ Investigational Agent(s)	Social Workers Addressing Firearm Risk (SAFR) Intervention – an online educational intervention to train practicing social workers how to recognize and respond to risks of gun violence among their clients.
IND/IDE #	N/A
Study Population	Practicing social worker adults in New York State
Sample Size	100 for each Aim; 200 total
Study Duration for individual participants	Aim 1: Two short surveys (30 minutes each) one month apart  Aim 2: 4-5 months
Study Specific Abbreviations/ Definitions	SAFR: Social Workers Addressing Firearm Risk  SSW: School of Social Work

## Objectives\*

*Describe the purpose, specific aims, or objectives of this research.*

Response:

Specific Aim 1: To test measurement tools that can be used to assess the efficacy of SAFR on theorized outcomes. Measures that have been used to assess similar

interventions for other professionals, notably medical doctors, will be modified for use with our population. The measures assess clinicians' firearm knowledge, attitudes, beliefs, and behaviors with clients. We will test these measurement tools with 100 practicing social workers recruited through professional networks, social media, and listservs. For all measures, we will address internal reliability, test-retest reliability, and construct validity, utilizing appropriate statistical procedures.

Specific Aim 2: Evaluate the preliminary efficacy of the SAFR intervention using a randomized controlled trial. An additional 100 practicing social workers (excluding participants from Aim 1) will be recruited, with  $n = 50$  allocated to each arm of the study utilizing block randomization. Participants in the control arm will receive invitations to all surveys but not to the SAFR intervention itself. We will utilize the validated measures from Aim 1 to assess changes on study variables. Results will be analyzed using either mixed linear models or generalized estimating equations as appropriate. Analyses will be performed with a focus on estimation of parameters for use in the planning of a subsequent comparative trial designed to fully assess intervention efficacy with a national sample. Supportive analyses that adjust for participant covariates will also be considered. We will also ask participants for feedback on the intervention and will track indicators of feasibility and acceptability (recruitment rates, completion of intervention and measurement tools).

*State the hypotheses to be tested, if applicable.*

*NOTE: A hypothesis is a specific, testable prediction about what you expect to happen in your study that corresponds with your above listed objectives.*

Response:

Aim 1: Our measurement tools will be reliable and valid assessments of study constructs.

Aim 2: The SAFR intervention will improve social workers' knowledge of gun violence, attitudes about social workers' need to intervene with all clients, and behaviors regarding discussing guns and gun violence risks with clients compared to pre-test and the control group. We also hypothesize that the SAFR intervention will be feasible and acceptable.

## **Scientific Endpoints\***

*3.1 Describe the scientific endpoint(s), the main result or occurrence under study.*

*NOTE: Scientific endpoints are outcomes defined before the study begins to determine whether the objectives of the study have been met and to draw conclusions from the data. Include primary and secondary endpoints. Some example endpoints are: reduction of symptoms, improvement in quality of life, or survival. Your response should **not** be a date.*

Response:

Aim 1 will be complete when we have measurement tools with satisfactory validity and reliability.

Aim 2 will be complete when the intervention has been completed by experimental group participants, and both control and experimental group participants have completed all measures in the pre-, post-, and follow-up-tests.

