## **Data Management and Analysis\***

*Describe the data analysis plan, including any statistical procedures. This section applies to both quantitative and qualitative analysis.*

Response:

Aim 1:

Items in all scales will be analyzed for variance and proper range. Scales will be examined for internal reliability, test-re-test reliability, content validity, and factorial reliability as appropriate. Any items or scales that demonstrate problematic results will be revised as needed before use in Aim 2.

Aim 2:

Scores on all scales will be compared over time (pre-, post-, and follow-up tests) and across groups (intervention/control groups) using either mixed linear models or generalized estimating equations as appropriate. Analyses will be performed with a focus on estimation of parameters for use in the planning of a subsequent comparative trial designed to fully assess intervention efficacy with a national sample. Supportive analyses that adjust for participant covariates will also be considered.

SPSS and SAS will be used for all analyses.

*If applicable, provide a power analysis.*

*NOTE: This may not apply to certain types of studies, including chart/records reviews, survey studies, or observational studies. This question is asked to elicit whether the investigator has an adequate sample size to achieve the study objectives and justify a conclusion.*

Response:

Not applicable at this time as the effect sizes from this intervention are unknown.

*Describe any procedures that will be used for quality control of collected data.*

Response:

We will check for proper importation from REDCap into downloaded datasets. We will also check that respondent answers are appropriately recorded per scale expectations.

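### Does the lack of a ranked Aim 2 outcome in Scientific Endpoints leave the efficacy estimate open to choice after the data are seen?

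*Combined protocol and SAP*

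**What the plan says.** The template field in Section 3.0, Scientific Endpoints, instructs the author as follows: "Include primary and secondary endpoints". For Aim 2 the reply is "Aim 2 will be complete when the intervention has been completed by experimental group participants", and when both arms have completed every survey. It names no variable, scale, time point or contrast.

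The content is found elsewhere:

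- **Study Summary.** The primary objective is "To evaluate the feasibility, acceptability, and preliminary effectiveness of the Social Workers Addressing Firearm Risk (SAFR) Intervention".
- **Section 2.0, Objectives.** The Aim 2 hypothesis expects improvement in knowledge, attitudes and "behaviors regarding discussing guns and gun violence risks with clients compared to pre-test and the control group". It continues: "We also hypothesize that the SAFR intervention will be feasible and acceptable". The Aim 2 text lists recruitment rates and completion of the course and measures as the feasibility and acceptability indicators.
- **Section 12.0, Procedures Involved.** The intervention arm's post-test adds questions about the course, and the hosting site retains data on non-completion, quiz results and time to completion.
- **Section 19.0, Data Management and Analysis.** For Aim 2, "Scores on all scales will be compared over time (pre-, post-, and follow-up tests) and across groups (intervention/control groups"), by mixed linear models or generalized estimating equations. The purpose is stated: "Analyses will be performed with a focus on estimation of parameters for use in the planning of a subsequent comparative trial". For Aim 1, "Any items or scales that demonstrate problematic results will be revised as needed before use in Aim 2".

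**The concern.** A completion condition is not an endpoint, and the field asks for endpoints. Reading on does not supply a ranking. The hypothesis names three constructs, the Aim 1 text adds a fourth (beliefs), and there are two assessments after baseline. Nothing says which of these leads. The hypothesis also sets pre-test and control side by side as comparators, which could be taken to leave the contrast open too.

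The estimates are meant to inform a larger trial. An estimate chosen because it is the largest of several is biased upward, whether or not a p-value is attached, and a sample size built on it would be too small. The plan also speaks of preliminary efficacy and states a directional hypothesis, so a reader may expect one result to be treated as the answer.

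**Working it through.** The plan contains no power calculation, significance level or effect size, so there is no stated figure to reproduce. The one sum available, 50 per arm × 2 = 100, agrees with the stated sample size. The check has two parts: how large the harm could be if it occurred, and whether the plan as written produces it.

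**1. Size, if the largest estimate were picked**

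Inputs from the documents: 50 per arm (Section 2.0); three constructs in the hypothesis; two assessments after baseline. Assumptions: one scale per construct, no dropout, equally correlated estimates. The number of scales is not known, because the instruments are in attachments.

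- Candidate between-arm estimates: 3 × 2 = 6.
- Standard error of an unadjusted standardised difference: √(2/50) = 0.20 SD. The 95% CI half-width is 1.96 × 0.20 = 0.39 SD.
- Expected maximum of six standard normal variables, by simulation: 1.267, 0.896 and 0.694 at correlation 0, 0.5 and 0.7.
- All true effects equal: the overstatement is that maximum × 0.20.
- Unequal true effects (assumed 0.6, 0.4, 0.4, 0.3, 0.2, 0.2 SD): the overstatement is the mean of the largest estimate minus its own true effect.
- Baseline adjustment, with an assumed pre-post correlation of 0.6: standard error 0.20 × √(1 − 0.6²) = 0.16 SD.

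| Mean overstatement (SD) | corr. 0 | corr. 0.5 | corr. 0.7 |
|---|---|---|---|
| Equal effects, SE 0.20 | 0.25 | 0.18 | 0.14 |
| Unequal effects, SE 0.20 | 0.18 | 0.10 | 0.05 |
| Unequal effects, SE 0.16 | 0.12 | 0.06 | 0.03 |

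The top row needs identical true effects on knowledge, attitudes and behaviour, which is unlikely. The bottom row is nearer to the planned models, which use the pre-test. Dropout would push the figures up again, and so would more scales: eight candidates (adding beliefs) with equal effects and SE 0.20 give 0.28, 0.20 and 0.16 SD.

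**2. Whether the written plan produces it**

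- *Selection.* Section 19.0 covers all scales at all three occasions. It does not say that one estimate is extracted, so the overstatement in the table does not apply to the full set of estimates.
- *Testing.* No significance level or success rule appears anywhere. A chance of at least one favourable result would describe a rule that the protocol does not have.
- *Comparator.* Aim 2 is randomised with a control arm. Comparing scores over time and across groups in a repeated-measures model is naturally a group-by-time analysis. The hypothesis joins pre-test and control with *and*, which fits that reading. The contrast is not written out, but an analyst would take change in one arm relative to the other.
- *Feasibility and acceptability.* The objective, hypothesis, indicators and data sources are all in other sections. Repeating them in Section 3.0 would add nothing to what is collected or reported.
- *Timing.* Aim 1 may alter items or scales before Aim 2, and the timeline in Section 13.0 puts that work in April and May, with Aim 2 recruitment from June. An exact scale could not sensibly be fixed in this version.

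**The case for a change.** The strongest case for a change is that it would cost only wording. The construct and time point could be named now and the exact scale locked after Aim 1. An estimation focus does not protect against selection, since the largest of several estimates is biased with or without a test. With assumed numbers, if every true effect were 0.40 SD and correlation were 0.5, the largest of six would average 0.40 + 0.18 = 0.58 SD. At two-sided 0.05 and 80% power, n per arm is 2 × (1.96 + 0.84)² / d², which is about 47 at 0.58 SD against about 99 at 0.40 SD.

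The textual point stands in full: Section 3.0 does not answer its own field, and no scale or time point is ranked. The arithmetic stands too, given its assumptions. What does not follow is that this trial's plan yields a wrong result. The example supposes that the planners of the next trial see all six estimates, take the largest, ignore an interval of about ±0.39 SD and make no allowance for having chosen it. Nothing in the protocol calls for that. Nor is a single lead efficacy estimate plainly right for a pilot of this size: statisticians differ on it, and a commitment to one scale at one time point before any effect has been seen has its own cost. The recall period of the behaviour items, which would bear on the choice of time point, is in attachments not available here.

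**Conclusion.** No change is needed. The Aim 2 entry in Section 3.0 is a poor answer to its field, and the ranking of scales and time points is missing detail. The analysis section nonetheless commits to all scales, all occasions and both arms, for estimation, so the plan followed as written gives a full set of sound randomised estimates from which later planners can work. The comparator is reasonably clear from the design, and the feasibility and acceptability indicators are already stated in other sections.

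The remaining exposure is selective emphasis when the results are written up or used. If the largest of six estimates were carried forward alone, the illustrative overstatement is about 0.03 to 0.25 SD. That range rests on one scale per construct, 50 per arm with no dropout, correlations of 0 to 0.7 between estimates, and the assumed true effects and pre-post correlation shown in the working. It measures a choice that someone might make later, not a property of the plan. The conclusion would differ if the documents stated a success rule, or said that one unnamed estimate would size the next trial; they do neither.

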## Background\*

*Provide the scientific or scholarly background, rationale, and significance of the research based on the existing literature and how it will contribute to existing knowledge. Describe any gaps in current knowledge. Include relevant preliminary findings or prior research by the investigator.*

Response:

Firearm violence remains a major problem in the United States, with annual deaths increasing in recent years. In 2020, 45,222 people died by firearms (Centers for Disease Control and Prevention [CDC], 2022a). The majority of those deaths (54%) were suicides; however, homicides have been on the rise. Mass shootings have also been rising recently, with 2019, 2020, and 2021 each setting new records according to the definition used by the Gun Violence Archive (2022). These deaths are not equally distributed among demographic groups; Black Americans, in particular, have very high rates of firearm deaths. Indeed, homicide is the leading cause of death for Black males ages 15-44 (CDC, 2022b). Beyond these deaths, an even larger number of people are seen in hospitals each year for firearm injuries, which can sometimes result in permanent disabilities in addition to serious mental health consequences (Kaufman et al., 2021). From a public health perspective, these deaths and injuries also affect individuals' families and communities, sometimes with devastating impacts.

While there are a number of policy measures that might address the problem of firearm violence, these solutions are not keeping up with increases in firearm injuries and vary widely across states. Thus, we must seek policy-neutral strategies to reduce firearm violence, including by training workers across multiple professions to discuss firearm safety. Social workers are already interfacing with many individuals who are at-risk of perpetrating or being victimized by firearms, including by suicide, but the scant evidence suggests that training opportunities are minimal both during and after their educational careers ([name] et al., 2018). In the only published survey of practicing social workers, conducted in one Midwestern state, only 34% of practicing social workers reported regularly assessing for firearm access and only 15.4% regularly counseled about firearm safety (Slovak et al., 2008). In a previous qualitative research project, we established that very few social workers in our region had received training before or after their degrees, and most expressed a desire to learn more ([name] et al., 2022). Few social work educational programs offer content in coursework to prepare social workers to address these issues (Feldman et al., 2006; Ruth et al., 2012). To our knowledge, there is no training program

related to firearms readily available to practicing social workers, and certainly none that are accessible through an online format to all social workers in the US.

*Include complete citations or references.*

Response:

Centers for Disease Control and Prevention (2022a). Web-based Injury Statistics Query and Reporting System (WISQARS) [Online]. National Center for Injury Prevention and Control, Centers for Disease Control and Prevention (producer). Available from <http://www.cdc.gov/ncipc/wisqars>

Centers for Disease Control and Prevention (2022b). Health Equity. [Website] Available from <https://www.cdc.gov/healthequity/lcod/index.htm>

Feldman, B. N., & Freedenthal, S. (2006). Social work education in suicide intervention and prevention: An unmet need?. *Suicide and Life-Threatening Behavior*, 36(4), 467-480.

Gun Violence Archive (2022). [Website] Available at: <https://www.gunviolencearchive.org/>

Kaufman, E. J., Wiebe, D. J., Xiong, R. A., Morrison, C. N., Seamon, M. J., & Delgado, M. K. (2021). Epidemiologic trends in fatal and nonfatal firearm injuries in the US, 2009-2017. *JAMA Internal Medicine*, 181(2), 237-244.

## Study Design\*

*Describe and explain the study design (e.g. case-control, cross-sectional, ethnographic, experimental, interventional, longitudinal, observational).*

Response:

Aim 1 is structured to provide essential tests required to establish measurement tools that are suitable to test the effectiveness of the SAFR intervention. Two surveys will be given one month apart, allowing for examination of test-retest validity.

Aim 2 is a randomized controlled trial of participation in the SAFR intervention. Participants complete pre- and posttests and a 3-month follow-up survey.

## Study Intervention/Investigational Agent

6.1 *Describe the study intervention and/or investigational agent (e.g., drug, device) that is being evaluated.*

Response: The Social workers Addressing Firearm Risk (SAFR) intervention was developed after in-depth reviews of current literature on firearm violence prevention and in collaboration with multiple researchers and experts across the country. It is a fully-online intervention that contains four modules that address the following topics: 1) The nature of firearm violence in the United States, including a basic introduction to firearm terminology and an examination of misconceptions about the nature of connection between mental illness and firearm violence; 2) a discussion of policies that are pertinent for mental health providers, such as the mechanism of mental health prohibitions, extreme risk protection orders, and reporting requirements in some states; 3) assessment tools and approaches for individuals at risk of firearm violence across multiple settings; and 4) community approaches to firearm violence prevention, including hospital-based programs. Each module includes interviews with experts, didactic content, handouts, and brief quizzes to check learning (required by New York State for continuing education credit).

*Drug/Device Handling: If the research involves drugs or device, describe your plans to store, handle, and administer those drugs or devices so that they will be used only on subjects and be used only by authorized investigators.*

*If the control of the drugs or devices used in this protocol will be accomplished by following an established, approved organizational SOP (e.g., Research Pharmacy SOP for the Control of Investigational Drugs, etc.), please reference that SOP in this section.*

Response: N/A

*If the drug is investigational (has an IND) or the device has an IDE or a claim of abbreviated IDE (non-significant risk device), include the following information:*

*Identify the holder of the IND/IDE/Abbreviated IDE.*

*Explain procedures followed to comply with sponsor requirements for FDA regulated research for the following:*

	Applicable to:		
FDA Regulation	IND Studies	IDE studies	Abbreviated IDE studies
21 CFR 11	X	X	
21 CFR 54	X	X	
21 CFR 210	X		
21 CFR 211	X		
21 CFR 312	X		
21 CFR 812		X	X
21 CFR 820		X	

Response:

N/A

